3.8.2 Secondary efficacy analyses

The secondary efficacy objectives in this study are to

- compare the two treatment arms with respect to overall survival
- evaluate the two treatment arms with respect to overall response rate and clinical benefit rate;
- describe time to response and duration of response in each treatment arm;
- evaluate the two treatment arms with respect to time to deterioration of ECOG Performance Status;
- evaluate patient reported outcomes for health-related quality of life in the two treatment arms.

OS is the key secondary endpoint. A hierarchical testing strategy, where OS is to be statistically evaluated and interpreted only if the primary efficacy endpoint PFS is statistically significant favoring the treatment arm, will be used to control the overall type-I error rate.

The analysis of all secondary efficacy endpoints will be performed based on the FAS.

3.8.2.1 Key secondary objective: overall survival

Comparing the overall survival (OS) between ribociclib+tamoxifen/NSAI+goserelin and placebo+tamoxifen/NSAI+goserelin is the key secondary objective in this study. OS is defined as the time from date of randomization to date of death due to any cause. A cut-off date will be established for each analysis of OS. If a patient is not known to have died by the date of analysis cut-off, then OS will be censored at the last contact date (see [Section 2.1.9](#)).

The analysis of OS will be based on the FAS. If the primary analysis of PFS is significant, the distribution of OS will be compared between the two treatment arms using a stratified log-rank test (strata based on IRT data) at one-sided 2.5% level of significance.

Up to 3 analyses may be performed for OS: (1) at the time of the primary analysis for PFS, at which point a total of 123 (49%) deaths are expected; (2) after approximately 189 (75%) deaths have been documented; and (3) a final analysis for OS after approximately 252 deaths. The type I error probability for OS tests will be controlled by using a Lan-DeMets (O'Brien- Fleming) alpha spending function at the one-sided $\alpha=0.025$ level (see [Section 3.14.2](#) for further details).

The distribution function of OS will be estimated using the Kaplan-Meier method and displayed for each treatment arm and stratum. The median OS along with 95% confidence intervals will be presented by treatment arm, along with the proportion of patients alive at selected time points and the associated 95% confidence intervals. The stratified Cox regression model, where the baseline hazard function is allowed to vary across strata, will be used to estimate the hazard ratio (HR) of OS, along with 95% confidence interval. Strata information will be obtained from the IRT.

[REDACTED]

[REDACTED]

Survival status, reason for censoring and death cause will be listed. Patients not known to have died will be censored for 'Loss to follow-up' if the time between their last contact date and the analysis cut-off date is longer than 12 + 2 weeks = 98 days (i.e. the planned interval between two OS follow-up visits plus the 1 week window on both sides).

Handling missing month/day in date of death

For rare cases when either day is missing or both month and day are missing for the date of death, the follow imputation rules will be implemented:

- If only day is missing, then impute max [(1 mmm-yyyy), min (last contact date +1, cutoff date)].
- If both day and month are missing, then impute max [(1 Jan-yyyy), min (last contact date +1, cutoff date)].

3.8.2.2 Overall response rate

ORR is defined as the proportion of patients with best overall response of confirmed complete response (CR) or confirmed partial response (PR) according to RECIST 1.1 (see Appendix 3 of the study protocol). ORR will be calculated based on the FAS using investigators' review of tumor assessment data. Patients with only non-measurable disease at baseline will be part of the analysis and will be included in the numerator only if a complete response was observed. ORR will be presented by treatment arm along with standard Wald asymptotic (i.e. normal approximation) 95% confidence intervals. The Cochran-Mantel Haenszel chi-square test (strata based on IRT data) will be used to compare the two treatment arms with respect to the ORR at a one-sided 2.5% level of significance.

As sensitivity analysis, ORR will be calculated and summarized including only patients with measurable disease at baseline.

As a supportive analysis, ORR will also be summarized based on the BIRC review of tumor data. However, no p-value will be presented.

Clinical benefit rate

CBR is defined as the proportion of patients with a best overall response of confirmed CR or PR, or SD lasting 24 weeks or longer, according to RECIST 1.1 criteria. A patient will be considered to have SD for 24 weeks or longer if a SD response is recorded at 24-1=23 weeks or later from randomization, allowing for the ± 1 week visit window for tumor assessments. Patients with only non-measurable disease at baseline will be part of the analysis and will be

included in the numerator only if they achieve a complete response or have a ‘Non-CR/Non-PD’ response 23 weeks or more after randomization. CBR will be calculated using the FAS based on the investigators’ tumor assessments. CBR will be summarized for the two treatment arms using descriptive statistics. The Cochran-Mantel-Haenszel test (strata based on IRT data) at one sided 2.5% level of significance will be used to compare the two treatment arms with respect to CBR.

As a sensitivity analysis, the above analyses will be repeated including only patients with measurable disease at baseline.

As a supportive analysis, CBR based on BIRC data will be summarized for the two treatment arms using descriptive statistics but no p-value.

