## **7.2 Assessment types**

### **7.2.1 Efficacy assessments**

#### **7.2.1.1 Imaging tumor assessments**

Tumor response will be assessed locally and centrally according to the Novartis guideline version 3.2 ([Appendix 3](#)) based on RECIST Version 1.1 ([Eisenhauer et al 2009](#)). Further details regarding blinded independent review committee (BIRC) assessment will be provided in the BIRC charter. The central review of the scans will be carried out in a blinded fashion for a randomly selected subgroup of patients (see [Section 9.3.6](#)). The decision regarding patient management will remain with the local investigator.

Patients should have at least one documented measurable lesion (per RECIST v1.1) or in the absence of measurable disease, have at least one predominantly lytic bone lesion at study entry.

Imaging assessments will be performed at screening within 28 days prior to randomization and subsequently every 8 weeks following randomization during the first 18 months and every 12 weeks until 36 months, then change to as clinically indicated. See [Table 7-2](#) for details of assessments. The 8-week, 12 week, or as clinically indicated interval should be respected regardless of whether study treatment is temporarily withheld.

After baseline, all assessments should be performed within  $\pm 7$  days of the scheduled day of assessment. The same method of assessment and the same technique should be used to characterize each individual and reported lesion at baseline and during follow up.

If a patient discontinues treatment for reasons other than radiological documentation of progression of disease, an efficacy assessment should be performed at the time of End of Treatment unless a CT/MRI for tumor measurement was performed within 21 days. Efficacy assessments should continue as per the scheduled visit per [Table 7-1a](#), [Table 7-1b](#) and [Table 7-2](#).

To the extent possible, each lesion should be assessed using the same imaging method throughout the study.

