All patients will undergo CT or MRI of the chest, abdomen and pelvis at baseline and subsequent scheduled visits per [Table 7-1a](#), [Table 7-1b](#) and [Table 7-2](#). The preferred imaging methodology is CT with intravenous (i.v.) contrast. However, if at baseline, a patient is known to have a contraindication to CT i.v. contrast media or develops a contraindication during the trial, a non-contrast CT of chest (MRI is not recommended due to respiratory artifacts) plus contrast-enhanced MRI (if possible) of abdomen and pelvis should be performed.

A whole body bone scan according to institutional guidelines (e.g. Tc-99 bone scan, whole body bone MRI, FDG-PET or sodium fluoride positron emission tomography (NaF PET)) should be acquired at baseline for all subjects if not collected previously within 42 days (6 weeks) prior to randomization. Skeletal lesions identified on the whole body bone scan at baseline, which are not visible on the chest, abdomen and pelvis CT (or MRI) scan should be imaged at baseline and followed at scheduled visits using localized CT, MRI or x-ray. Whole body bone scans need not be repeated after baseline unless clinically indicated.

Color photography, including a metric ruler to estimate the size of the lesion, must be acquired for all **skin lesions** present at baseline per instructions provided in the manual from the designated vendor. These should be followed throughout the study according to the schedule outlined in [Table 7-2](#).

Other metastatic disease sites will be followed by CT or MRI, as clinically indicated.

Chest x-ray or ultrasound should not be used to assess tumor lesions. Partial Response (PR) and Complete Response (CR) must be confirmed by repeat assessments performed not less than 4 weeks and after the criteria for objective response are first met. In case tumor assessment is performed <8 weeks from the first assessment of an objective response to confirm PR/CR, subsequent tumor assessments should revert back to the protocol schedule outlined in [Table 7-1a](#). Positron Emission Tomography (PET)/CT may be used only if the CT component is of similar diagnostic quality as a CT performed without PET, including the utilization of oral and i.v. contrast media. At the discretion of the Investigators, FDG-PET scans may be performed to document progressive disease per RECIST 1.1 ([Appendix 3](#)). If possible, a single radiologist

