2.5.3 Best overall response (BOR)

The best overall tumor response will be assessed per RECIST 1.1 criteria. The definitions and the details on the derivation are given in Appendix 3 of the Clinical Study Protocol.

Only tumor assessments performed before the start of any further anti-neoplastic therapies (i.e. any additional anti-neoplastic therapy or surgery) and within 30 days after the last administration of study treatment will be considered in the assessment of best overall response. Further anti-neoplastic therapies will be identified from the data collected on 'Anti-neoplastic

therapies since discontinuation of study treatment' CRFs. Palliative radiotherapy is the only setting of radiotherapy allowed during the study. Therefore, palliative radiotherapy will not be considered as an anti-neoplastic therapy for assessment of BOR. Continuation of combination partner therapy alone after end of study treatment will also not be considered as a new anti-neoplastic therapy.

The standard definition of a best overall response evaluation of 'stable disease', 'disease progression' or 'unknown' given in the Appendix 3 of the Clinical Study Protocol will be used for this study. Best overall response for each patient is determined from the sequence of overall (lesion) responses (as reported by the investigator for local BOR, and as reported by BIRC for central BOR) according to the following rules:

- CR = at least two determinations of CR at least 4 weeks apart before progression.
- PR = at least two determinations of PR or better at least 4 weeks apart before progression (and not qualifying for a CR).
- SD = at least one SD assessment (or better) > 6 weeks after randomization (and not qualifying for CR or PR).
- Non-CR/non-PD = at least one non-CR/non-PD assessment (or better) > 6 weeks after randomization date (and not qualifying for CR). This applies only for patients with non-measurable disease alone at baseline.
- PD = progression ≤ 12 weeks after randomization (and not qualifying for CR, PR, SD or Non-CR/non-PD).
- UNK = all other cases (i.e. not qualifying for confirmed CR or PR and without SD or Non-CR/Non-PD after more than 6 weeks or progression within the first 12 weeks).

Patients with best overall response "unknown" will be summarized by reason for having unknown status. The following reasons will be used:

- No valid post-baseline assessment
- All post-baseline assessments have overall response UNK

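### Read literally, the SAP's CBR rule scores a first PR at about week 24 that is never confirmed and has no later SD as no clinical benefit, while SD at week 24 with the same later course counts as benefit

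*SAP*

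**What the plan says.** The SAP for the primary analysis, under Clinical benefit rate within Section 3.8.2.2, states: "CBR is defined as the proportion of patients with a best overall response of confirmed CR or PR, or SD lasting 24 weeks or longer". It then says how the duration condition is to be programmed: "A patient will be considered to have SD for 24 weeks or longer if a SD response is recorded at 24-1=23 weeks or later". Patients with only non-measurable disease count if they reach CR or have a Non-CR/Non-PD "response 23 weeks or more after randomization". The arms are compared by a stratified Cochran-Mantel-Haenszel test at one-sided 2.5%. The analysis is repeated in patients with measurable disease and summarised without a p-value on BIRC data.

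Section 2.5.3 of the same SAP gives the BOR rules. For stable disease: "SD = at least one SD assessment (or better) > 6 weeks after randomization (and not qualifying for CR or PR". For partial response: "PR = at least two determinations of PR or better at least 4 weeks apart before progression". It also limits which scans are usable: "Only tumor assessments performed before the start of any further anti-neoplastic therapies", and within 30 days of the last dose.

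Protocol Section 7.2.1.1 schedules imaging "subsequently every 8 weeks following randomization during the first 18 months", with a window of 7 days either way, and adds: "Partial Response (PR) and Complete Response (CR) must be confirmed by repeat assessments performed not less than 4 weeks".

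The week-23 rule belongs to the SAP. Protocol Section 10.5.2.2 asks only for 24 weeks of stable disease and does not say how to establish it. The SAP for the final report lists CBR as an endpoint but has no derivation rule, so the primary-analysis SAP is the only place where the rule is spelled out.

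**The concern.** The two rules treat an improvement differently. For BOR, a single PR counts as at least SD. For the 24-week limb of CBR, only a scan recorded as SD counts. A patient whose tumour shrinks enough at week 24 to be called PR therefore stops meeting the SD condition at the scan that decides it. If nothing rescues her later, she is ranked below a patient whose tumour did not shrink to that degree. An endpoint meant to capture disease control should not reverse that order.

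CBR is a secondary endpoint with a formal between-arm test, so its derivation should not depend on how a programmer reads one sentence. The non-measurable limb has the same gap if a CR there must also be confirmed: Non-CR/Non-PD at weeks 8 and 16 followed by one unconfirmed CR at week 24 would fail.

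**Working it through.** **The plan's own figure.** The week threshold reproduces: 24 weeks minus the 1-week visit window = 24 − 1 = 23. This matches the early limit of week 23 for the C7D1 scan in SAP Table 2-3.

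**Inputs.** Scans at weeks 8, 16, 24, 32 and so on (Protocol 7.2.1.1); confirmed PR = two determinations at least 4 weeks apart before progression (SAP 2.5.3); BOR of SD = one SD or better after week 6 (SAP 2.5.3); CBR = confirmed CR/PR, or a recorded SD at week 23 or later (SAP 3.8.2.2).

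**Rules applied.** Every sequence below starts with SD at weeks 8 and 16.

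| Scans from week 24 | BOR | CBR, literal rule | CBR, SD or better |
|---|---|---|---|
| SD at 24 | SD | benefit | benefit |
| PR at 24, no later usable scan | SD | **no benefit** | benefit |
| PR at 24, PD at 32 | SD | **no benefit** | benefit |
| PR at 24, UNK at 32, nothing usable after | SD | **no benefit** | benefit |
| PR at 24, SD at 32 | SD | benefit | benefit |
| PR at 24, PR at 28 | PR | benefit | benefit |
| PR at 24, PR at 32 | PR | benefit | benefit |
| SD at 24, PR at 32, PD at 40 | SD | benefit | benefit |

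Of the six continuations after a first PR at week 24, the literal rule loses three and counts three. Two further cases mark the edges:

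- PR at 24, UNK at 32, PR at 40 has two PRs 16 weeks apart before progression, so it is a confirmed PR and counts.
- In the last row the first PR comes after week 24. The week-24 SD already qualifies, so whether that PR is confirmed does not matter.

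**How a patient can have no later usable scan.** SAP Section 2.4 removes scans after new antineoplastic therapy from CBR, and Section 2.5.3 removes scans more than 30 days after the last dose from BOR. A patient who responds at week 24 and then stops treatment may have nothing eligible at week 32.

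**Size.** The documents give no frequency. With 672 patients randomized 1:1, each arm has about 672 / 2 = 336. If a share f of an arm follows one of the excluded patterns (assumed range):

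- f = 0.5%: 336 × 0.005 = 1.7 patients
- f = 1%: 336 × 0.01 = 3.4 patients
- f = 3%: 336 × 0.03 = 10.1 patients

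CBR in that arm is lower by the same 0.5 to 3 percentage points. The between-arm difference moves only by the difference in loss. With assumed true rates of 70% (control) and 80% (test), equal losses of 1% leave the difference at 79 − 69 = 10 points. Losses of 1% in control and 3% in test give 77 − 69 = 8 points; the reverse gives 79 − 67 = 12 points. At one-sided 2.5%, illustrative power is 85% with no loss, 84% with 1% lost in each arm, and 65% in the 8-point case. None of these rates comes from the documents.

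**The case against.** The best defence is that the intended meaning can be recovered. SAP Section 2.4 lists CBR among the analyses based on BOR, and the BOR rule for SD accepts a better response. Protocol Appendix 3 (Section 3.2.6) defines duration of stable disease over CR, PR and SD together, ending as time to progression does, so an improvement does not end stability. A careful programmer may have carried this over. That stands as evidence of intent and supports the fix. It does not cure the text: the CBR sentence is explicit, it names SD alone, and Appendix 3 is a general guideline whose own CBR definition does not mention a better response either.

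A reader might also infer more than the documents support:

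- *Every unconfirmed week-24 PR is lost.* No. Under Appendix 3, Section 3.1, a single PR that falls back below a 30% reduction without progression is scored SD at the next scan, and that SD qualifies.
- *The rule works against the arm with more late responses.* This does not follow. First responses after week 24 normally come after a qualifying SD; they are exposed only if the week-24 scan was missed or unknown. What matters is a week-24 PR followed at once by progression or by no usable scan, and nothing in the documents says which arm has more of these.
- *CBR depends materially on the cut-off date.* Unlikely. The last patient was randomized on 01-Aug-2016, so her week-24 and week-32 scans fall on about 16-Jan-2017 and 13-Mar-2017. The cut-off date is not stated, but it was still being projected on 24-Feb-2017 and the primary analysis was in October 2017.

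Finally, CBR lies outside the PFS/OS hierarchy and has no stated power. That limits the consequence, and rightly so.

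**Conclusion.** The point holds in a narrow form. As written, the CBR rule ranks one pattern the wrong way round: SD, SD, then a first PR at about week 24 that is never confirmed and is followed by no recorded SD. This rests on reading the sentence as it stands and on the 8-weekly schedule; it needs no assumption about the data. How many patients are affected, and whether the arms differ, cannot be derived from the documents. The 2 to 10 patients per arm and the power figures are illustrations on assumed rates and should not be cited as estimates of bias. PFS, OS and ORR do not use this rule. It is a small error on a tested secondary endpoint and worth correcting because correction costs almost nothing.

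**What to change.** Replace the sentence in the Clinical benefit rate text of SAP Section 3.8.2.2 with a rule to this effect:

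*The 24-week condition is met if an overall lesion response of SD or better (Non-CR/Non-PD or better for patients with non-measurable disease only) is recorded at 23 weeks or later from randomization, before progression and among the assessments eligible for BOR.*

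The limits on progression and eligibility are needed; without them, scans after progression or after new therapy could qualify. State that the BIRC-based CBR uses the same rule. The measurable-disease sensitivity analysis inherits it, because the SAP has that analysis repeat the main one.

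The primary analysis has already been run, so the sponsor should also record which reading was programmed. If it was the literal one, rerun CBR and report the number of reclassified patients in each arm; that count replaces the assumed range above.

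Cost: one sentence in the SAP, one condition in the derivation program and, if needed, a rerun of the CBR tables. No new data are required.

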3.8.2.3 Time to response

Time to response (CR or PR) is the time from date of randomization to first documented response (CR or PR, which must be confirmed subsequently) according to RECIST 1.1. All patients in the FAS will be included in the time to response calculation. Patients who did not achieve a confirmed PR or CR will be censored at:

- the maximum follow-up time (i.e. FPFV to LPLV used for the analysis) for patients who had a PFS event (i.e. either progressed or died due to any cause);
- the last adequate tumor assessment date for all other patients.

Time to response data will be listed and summarized by treatment arm. The distribution of time to response will be estimated using the Kaplan-Meier method and the median time to response will be presented along with 95% confidence interval only if a sufficient number of responses is observed. A descriptive summary of time to response for the responders will also be presented. No inferential analysis that compares time to response between the two treatment arms will be performed.

3.8.2.4 Duration of response

DoR applies only to patients whose best overall response was CR or PR. The start date is the date of first documented response (CR or PR, which must be confirmed subsequently) and the end date is the date of event defined as the first documented progression or death due to underlying cancer. The start date will be determined using the time the response was first determined and not using the time the response was confirmed. If a patient has not had an event, duration is censored at the date of last adequate tumor assessment, using the same censoring rules described for primary PFS analysis. DoR will be summarized by treatment arm. The distribution of duration of response will be estimated using the Kaplan-Meier method and the median response duration will be presented along with 95% confidence interval only if a sufficient number of responses is observed. No inferential analysis that compares the DoR between the two treatment arms will be performed.

3.8.2.5 ECOG performance status

The ECOG PS scale ([Table 3-4](#)) will be used to assess physical health of patients, ranging from 0 (most active) to 5 (least active):

Table 3-4 ECOG Performance Scale

Score	Description
0	Fully active, able to carry on all pre-disease performance without restriction
1	Restricted in physically strenuous activity but ambulatory and able to carry out work of a light or sedentary nature, e.g., light house work, office work
2	Ambulatory and capable of all self-care but unable to carry out any work activities. Up and about more than 50% of waking hours
3	Capable of only limited self-care, confined to bed or chair more than 50% of waking hours
4	Completely disabled. Cannot carry on any self-care. Totally confined to bed or chair
5	Dead

The following intervals will be used to group the ECOG PS data over time. Day in columns 2 and 3 is defined as date of ECOG PS assessment date – randomization date + 1. The correspondence with Day in column 1 assumes that a patient is treated on the day of randomization; however the definition of Day in columns 2 and 3 still applies if this is not the case, i.e. randomization date is taken as the reference for the windows.

Table 3-5 Time windows for ECOG PS assessments

Assessment	Target day of assessment	Time Interval
Baseline		Day 1 (if not available use screening)
Cycle 1 Day 15	15	Day 2 to day 21
Cycle 2 Day 1	29	Day 22 to day 42
Cycle 3 Day 1	57	Day 43 to day 63
Cycle 3 Day 15	71	Day 64 to day 77
Cycle 4 Day 1	85	Day 78 to day 98
Cycle k Day 1 (k≥5)	$d=(k-1)*28+1$	Day d-14 to day d+13
End of Treatment		Assessment taken at the end of treatment visit

If more than one assessment is done within the same time window, the assessment performed closest to the target date will be used. If 2 assessments within a time window are equidistant from the target date, then the worst of the 2 assessments will be used.

Frequency counts and percentages of patients in each score category will be provided by treatment arm and time point.

An analysis of time to definitive deterioration of performance status will be performed. The time to definitive deterioration is calculated from the date of randomization. Deterioration is defined as an increase in ECOG PS by at least one category from the baseline score or death due to any cause. Deterioration is considered definitive if no return to baseline or better in ECOG PS is observed subsequent to the deterioration during the treatment period.

If a definitive deterioration is observed after two or more missing assessments (using an analogous rule to that defined for PFS in [Section 2.5.5](#), based on the windows specified above),

time to deterioration will be censored at the date of the last ECOG PS assessment prior to the deterioration.

Patients receiving any further anti-neoplastic therapy before definitive deterioration will be censored at the date of their last assessment before the start date of the therapy. Patients that have not deteriorated as of the cutoff date will be censored at the date of their last assessment before the cutoff.

Kaplan-Meier estimates will be constructed for each treatment arm. The median, 25th and 75th percentiles for time to definitive deterioration for each treatment group will be obtained along with 95% confidence intervals.

A stratified log-rank test at one-sided 2.5% level of significance will be used to test the difference in time to definitive deterioration of performance status between treatment arms. A (stratified) Cox proportional hazards model will be used to estimate the hazard ratio (with 95% confidence interval).

